# 1. Version History

| Version | Summary of Changes  | Author(s)/Title  |
|---------|---|--|
| 1.0     | Not Applicable, New Document  | [name], Sr. Statistician
[name], Sr. Statistician      |
| 2.0     | 
 
Added description of events required to
demonstrate the primary objective of the study in
section 6.1
 
Clarified that mentioned attrition and crossover
rates are for each treatment group in section 6.2
 
 | [name], Sr. Statistician
[name], Pr. Statistician |

2. List of Abbreviations and Definitions of Terms

This document is electronically controlled. Printed copies are considered uncontrolled.

Version 2.0 15/MAY/2017

| Abbreviation | Definition   |  |
|--------------|--|--|
| AE           | Adverse Event                                      |  |
| AF           | Atrial Fibrillation                                |  |
| AT           | Atrial Tachycardia                                 |  |
| CABG         | Coronary Artery Bypass Grafting                    |  |
| CEC          | Clinical Events Committee                          |  |
| CIP          | Clinical Investigation Plan                        |  |
| CRF          | Case Report Form (synonymous with eCRF)            |  |
| CRT          | Cardiac Resynchronization Therapy                  |  |
| СТ           | Computerized Tomography                            |  |
| ECG          | Electrocardiogram                                  |  |
| eCRF         | electronic Case Report Forms (synonymous with CRF) |  |
| ICD          | Implantable Cardioverter Defibrillator             |  |
| ICM          | Insertable Cardiac Monitor                         |  |
| IS           | Ischemic Stroke                                    |  |
| ITT          | Intention To Treat                                 |  |
| LA           | Left Atrial  |  |
| LAA          | Left Atrial Appendage                              |  |
| LVEF         | Left Ventricular Ejection Fraction                 |  |
| MRI          | Magnetic Resonance Imaging                         |  |
| NIH          | National Institutes of Health                      |  |
| OAC          | Oral anticoagulation                               |  |
| РР           | Per Protocol                                       |  |

This document is electronically controlled. Printed copies are considered uncontrolled.

| RDC | Remote Data Capture       |
|-----|---------------------------|
| SAP | Statistical Analysis Plan |
| SOC | System Organ Class        |
| ТІА | Transient Ischemic Attack |

# 3. Introduction

The purpose of the Stroke AF study is to compare the incidence of atrial fibrillation (AF) through 12 months by continuous cardiac rhythm monitoring with the Reveal LINQ™ Insertable Cardiac Monitor (ICM) (continuous monitoring arm) vs standard of care (SoC) medical treatment (control arm) in subjects with a recent ischemic stroke of presumed known origin. AF will be defined as an AF event lasting more than 30 seconds and adjudicated by the endpoint adjudication committee.

The study is conducted at approximately 40 sites located in the United States (U.S.) and approximately 496 subjects are being enrolled in the study. A total of 23 first documented AF events within 12 months of randomization are required for the study to test the primary objective. In addition, a guidance was sent to sites stating that a maximum of 3 subjects with lacunar stroke (i.e. small vessel disease) may be enrolled at each site. This restriction is not in the CIP.

The enrollment period started in April 2016 and will take approximately 20 months. Subjects will be followed for 3 years, until end of device life or until official study closure, whichever occurs first. Therefore, the expected study duration from first enrollment to official study closure (final report) is approximately 4.5 years. The duration of individual subject participation will vary based on timing of site activation and their enrollment; however, participation of an individual subject will be for 3 years, until end of device life or until study closure, whichever occurs first.

This Statistical Analysis Plan (SAP) has been designed to document, before data is analyzed, the rationale for the study design, and the planned analyses that will be included in a 12-month follow-up study report related to the primary objective (primary report), and a final report related to the secondary objective. This SAP does not limit the analysis in reports, and additional analysis of the study data beyond this plan is expected.

The Stroke AF CIP Version 2, dated 27/JAN/2016 was used to create this SAP.

# 4. Study Objectives

The Stroke AF study will compare the incidence rate of AF through 12 months between continuous monitoring and standard of care in subjects with a recent ischemic stroke of presumed known origin. Subjects will be randomized 1:1 to the continuous monitoring arm or control arm.

This document is electronically controlled. Printed copies are considered uncontrolled.

Version 2.0 15/MAY/2017

### 4.1. Primary objective

To compare the incidence rate of AF through 12 months between the continuous monitoring arm vs control arm in subjects with a recent ischemic stroke of presumed known origin.

### 4.2. Secondary objective

To compare the incidence rates of AF through the duration of study follow-up between study arms.

### 4.3. Primary and final reports

The objectives for the primary report can be analyzed after all enrolled subjects have 1) had their 12month visit, 2) missed the 12-month visit and the 12-month visit window has closed, or 3) exited prior to the 12-month visit window closing. A data snapshot will be used to analyze data for the primary report since follow-up will continue. Once follow-up is complete and the study data collection and cleaning is finalized, a second data snapshot will be used to analyze data for the final report.

Table 1 shows which objectives will be analyzed for the primary and final reports. All objectives will be included in the final report using the final data snapshot.

| l able 1 | L: Objective | s analyzed fo | or the primary | and final reports |
|----------|--------------|---------------|----------------|-------------------|
|          |              |               |                |                   |

| Objective           | Primary Report | Final Report |
|---------------------|-----------------------|--------------|
| Primary Objective   | Х                     | Х            |
| Secondary Objective |                       | Х            |

# 5. Investigation Plan

### 5.1 Study Design and background information

The Stroke AF study is a prospective, multi-site, randomized, controlled, non-blinded, post-market study, comparing the incidence rate of Atrial Fibrillation (AF) through 12 months between continuous cardiac monitoring and standard of care in subjects with a recent ischemic stroke (IS) of presumed known origin. No interim analyses are planned.

Most patients with IS are treated with anti-platelet (AP) therapy. However, patients with IS who have been diagnosed with AF are normally treated with long-term oral anticoagulation (OAC) as OAC is dramatically more effective at preventing recurrent IS than AP therapy in patients with AF. Therefore, detection of AF after IS crucial, as it results in an important change in the administration of antithrombotic therapy from AP to OAC, thereby reducing the risk of recurrent stroke. The CRYSTAL AF study demonstrated that continuous monitoring via the Reveal LINQ ICM is superior to standard of care for detecting AF after cryptogenic stroke. However, it remains unclear what the long-term rate of AF is in the IS patient population with a presumed known origin. The results of the Stroke AF clinical study will then provide evidence that could impact the treatment and long-term prognosis for patients classified as having an IS of presumed known origin by demonstrating the value of long term monitoring for AF in this patient population.

This document is electronically controlled. Printed copies are considered uncontrolled.

Version 2.0 15/MAY/2017

### Page 7 of 17

### 5.2 Eligibility

The inclusion and exclusion criteria to be enrolled into the study are as follows:

### Inclusion criteria

- Subject has had an ischemic stroke believed to be due to small vessel disease, large vessel cervical or intracranial atherosclerosis within the past 10 days
- Subject is willing and able to undergo study requirements and expected to be geographically stable during study follow-up
- Subject is 60 years of age or older, or age 50 to 59 years plus a documented medical history of at least one of the following additional risk factors for stroke:
  - Congestive heart failure
  - Hypertension (Systolic Blood Pressure >140)
  - Diabetes Mellitus
  - Prior Stroke (>90 days ago, other than study qualifying index event)
  - Vascular disease (e.g. coronary artery disease, heart attack, peripheral artery disease and complex aortic plaque)

### **Exclusion criteria**

- Subject has had a cryptogenic stroke
- Subject has had a cardioembolic stroke
- Subject has untreated hyperthyroidism
- Subject has had a recent myocardial infarction <1 month of stroke
- Subject has had a recent cardiac surgery (e.g. coronary artery bypass surgery (CABG)) <1 month of stroke
- Subject has a mechanical heart valve
- Subject has valvular disease requiring immediate surgical intervention
- Subject has documented prior history of atrial fibrillation or atrial flutter
- Subject has permanent indication for oral anticoagulation
- Subject has permanent contraindication to oral anticoagulation such that detection of AF would not change medical management, based on enrolling investigators judgment
- Subject is enrolled in a concurrent study that may confound the results of this study. Co-enrollment in any concurrent clinical study (including registries) requires approval of the study manager or designee.
- Subject's life expectancy is less than 1 year
- Subject is pregnant
- Subject has or is indicated for implant with a pacemaker, ICD, CRT, or an implantable hemodynamic monitor
- Subject with a medical condition that precludes the patient from participation in the opinion of the investigator

This document is electronically controlled. Printed copies are considered uncontrolled.

Version 2.0 15/MAY/2017

### 5.3. Treatment and Study Procedures

### 5.3.1. Treatment

Subjects are randomized 1:1 to the continuous monitoring arm or the control arm. Subjects randomized to the continuous monitoring arm will have a Reveal LINQ ICM inserted within 10 days of the qualifying stroke and undergo continuous remote monitoring. Subjects randomized to the control arm will be followed per site specific standard of care.

### 5.3.2. Study Procedures

Data will be collected via electronic Case Report Forms (eCRF), Reveal LINQ ICM device interrogation files and Medtronic CareLink transmissions. A web-based application tool, Remote Data Capture (RDC), will be used for data entry of the eCRF. Clinical data will be collected at baseline, 1, 6 and 12 months postrandomization, and then at recurring 6 months intervals until study exit. Additionally, subjects randomized to the continuous monitoring arm will have data collected at REVEAL LINQ ICM insertion, 3 and 9 months.

# 6. Determination of Sample Size

### 6.1. Primary Objective

A total of 23 first events across the two treatment groups are required to demonstrate the primary objective of the study. Assuming 2% attrition from enrollment to randomization, approximately 486 subjects will be randomized. Subjects will be followed for 3 years, until end of device life or until official study closure, whichever occurs first. However, the primary objective of the study, upon which this sample size calculation is based, will be analyzed considering data up to the 12 months follow-up visit for all subjects in the study at the time of the analysis. This sample size calculation then assumes a follow-up time equal to 1 year and an accrual time equal to zero (data from all subjects is analyzed from randomization to the 12th month follow-up visit, regardless of how long they've been in the study at the time of the analysis). Withdrawn subjects will not be replaced.

The assumptions used for the calculations were:

- Two-sided log-rank test
- Alpha = 0.05
- 85% power
- Annual Attrition rate = 10% (in each treatment group)
- Annual Crossover rate = 5% (in each treatment group)
- Follow-up Time = 1 year
- Event-free one-year survival rate of 92% in the continuous monitoring arm
- Event-free one-year survival rate of 98% in the control arm (hazard ratio of 4.13)

This document is electronically controlled. Printed copies are considered uncontrolled.

Version 2.0 15/MAY/2017

The procedure "Logrank tests (Lakatos) using proportion surviving" in PASS 2008 was used to calculate the number of events required to test this objective.

### 6.2. Secondary Objective

A number of 486 subjects randomized to achieve the primary objective and the assumptions below will also ensure 100% power to test the **secondary objective** of the study.

The assumptions used for the calculations were:

- Two-sided log-rank test
- Alpha = 0.05
- Annual Attrition rate = 10% (in each treatment group)
- Annual Crossover rate = 5% (in each treatment group)
- Accrual Time = 2 years
- Follow-up Time = 3 years
- Event-free survival rate of 80% in the continuous monitoring arm
- Event-free survival rate of 97% in the control arm (hazard ratio of 7.33)

The procedure "Logrank tests (Lakatos) using proportion surviving" in PASS 2008 was used to calculate the power to test this objective.

# 7. Statistical Methods

### 7.1 Study Subjects

### 7.1.1. Disposition of Subjects

A subject is enrolled in the study when he/she signs and dates the Patient Informed Consent. The subject is then eligible for randomization assignment after study enrollment and verification of eligibility criteria. Enrollment, randomization and insertion of the Reveal LINQ ICM must occur within 10 days of the qualifying stroke event. Once a subject is assigned to a study arm, he is considered eligible. A flow chart similar to Figure 1 will be created to describe patient disposition.

Study exits will be summarized according to exit reason. Violation of inclusion and exclusion criteria at baseline will be summarized for all enrolled patients.

The following tables will be considered to summarize patient disposition:

- 1. Number (%) of patients per center and randomization group
- 2. Number (%) of patients by visit and randomization group
- 3. Follow-up time per randomization group

Follow-up time will be determined as the time between date of enrollment and date of study exit or date of last contact with subject if the subject was lost to follow-up.

This document is electronically controlled. Printed copies are considered uncontrolled.

Version 2.0 15/MAY/2017

### 7.1.2. Clinical Investigation Plan (CIP) Deviations

Deviations from the clinical investigation plan will be collected on the Study Deviation eCRF. Deviations will be summarized in the final report in a table by coded category. Deviation coding will be performed by Medtronic, and the coding will be collected on the Medtronic Use Only Deviation eCRF. The number of deviations per category, and the number and percentage of subjects with a deviation in each category will be reported.

### 7.1.3. Analysis Sets

The following analysis sets will be used in this study:

This document is electronically controlled. Printed copies are considered uncontrolled.

Enrollment Cohort: All subjects who signed the informed consent and meet inclusion/exclusion criteria.

**Intent to Treat (ITT) Cohort:** Enrolled subjects who are randomized, according to the treatment arm to which they were randomized.

**Per Protocol (PP) Cohort:** All subjects who fulfill the protocol as follows:

- In ITT cohort (i.e., meets inclusion/exclusion criteria, gave informed consent, and was randomized)
- Exclude subjects that cross-over to the other arm
- Exclude subjects that are not programmed as follows at any point during the study (from CIP):
  - Reason for Monitoring = Cryptogenic Stroke
  - AF Detection Sensitivity = Balanced Sensitivity
  - Ectopy Rejection = Aggressive
  - AT/AF Recording Threshold = All Episodes
  - Type of AT/AF Detection = AF Only

The ITT Cohort will be used to analyze the primary and secondary objectives. The use of the PP Cohort will be specified in each evaluation objective.

Table 2 below shows the use of each analysis set:

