8.4.7. Study Exit

A study exit e-CRF is required for all subjects except in the case of death. Prior to exiting a subject from the study, it is recommended to follow the subject until all ongoing system and/or procedure related AEs are resolved or unresolved with no further actions planned. Following exit, subjects should continue to receive standard medical care. Upon exiting from the study, no further study data will be collected or study visits will occur for the subject. All data available through the time of the subject's exit will be used for analysis.

Subjects are urged to remain in the study as long as possible but may be exited from the study for any of the following situations:

- Subject lost to follow-up
- Subject did not meet inclusion/exclusion criteria and not randomized
- Subject not randomized
- Subject did not provide consent or data use protection authorization

18 December 2018 Version 4.0 Page 35 of 66

- Subject chooses to withdraw (e.g., consent withdrawal, relocation to another geographic location)
- Investigator deems withdrawal necessary (e.g., medically justified, inclusion/exclusion criteria not met, failure of subject to maintain adequate study compliance)
- Subject with a Reveal LINQ ICM that has reached end of device life (continuous monitoring patients only)
- Subject has completed 3 years of follow-up
- Study Closure

The following information is required to be collected at study exit on the study exit e-CRF:

- Date of exit
- Reason for exit
- Reveal LINQ Interrogation (if available, subjects with a Reveal LINQ ICM inserted only)
- AF Assessment (except in the case of lost to follow-up or death)
- Stroke/TIA Assessment (except in the case of lost to follow-up or death)

In the case that the subject is determined to be lost to follow-up, details of a minimum of two attempts and the method of attempt (e.g., one letter and one phone record or two letters) to contact the subject must be documented. In addition, follow the regulations set forth by the governing Ethics Committee.

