Arrhythmic episodes recorded by the subject's inserted/implanted device or from external monitoring will be adjudicated by the adjudication committee to determine if they meet the primary endpoint definition. Only first detected and adjudicated AF episodes within 12-months (365 days) will be included for analysis. Each subject's time to first detected and adjudicated AF will be defined as the time from randomization date to the date of first documented AF (i.e. the date of event per Reveal LINQ ICM, ECG, etc) to meet the primary endpoint definition, and Kaplan-Meier curves will be generated for each randomization arm. Subjects who have not experienced an AF endpoint through 12 months will be censored at:

- their point of last contact, usable Reveal LINQ ICM interrogation or CareLink transmission if they occur before 12 months, whichever is later or
- 12 months if their point of last contact, usable Reveal LINQ ICM interrogation or CareLink transmission go beyond 12 months.

A two-sided log-rank test will be performed to compare the rates between arms.

In addition to the analysis on the full population, subgroup analysis for subjects with small vessel disease stroke and large vessel cervical or intracranial atherosclerosis stroke will be presented.

- vii. Determination of Patients/Data for Analysis
- All randomized subjects will be included in the analysis.

18 December 2018 Version 4.0 Page 52 of 66

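### SAP 7.1.3 restates ITT with an eligibility condition, so randomized subjects later found ineligible could be left out of a primary analysis that the protocol says includes everyone randomized

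*SAP*

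**What the plan says.** SAP 7.9 (Primary Objective, v) analyses the primary objective in the ITT cohort. SAP 7.1.3 describes that cohort in two ways.

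- The ITT line has no eligibility condition: "Enrolled subjects who are randomized, according to the treatment arm to which they were randomized".
- The first per-protocol criterion explains ITT in a parenthesis that has one: "In ITT cohort (i.e., meets inclusion/exclusion criteria, gave informed consent, and was randomized".

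The ITT line depends on what enrolled means, and the SAP gives two meanings.

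- The Enrollment Cohort in SAP 7.1.3 is "All subjects who signed the informed consent and meet inclusion/exclusion criteria".
- SAP 7.1.1 says "A subject is enrolled in the study when he/she signs and dates the Patient Informed Consent". Protocol 7.2 likewise defines enrollment by consent alone.

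Protocol 12.1 (vii) is unconditional: "All randomized subjects will be included in the analysis". Protocol 8.3 keeps subjects in their assigned arm on an intention-to-treat basis, and protocol 8.4.7 uses data collected up to exit.

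**The concern.** If the eligibility condition is applied, a subject who was randomized and later found not to meet the criteria is outside ITT, and so outside the primary analysis. Under SAP Table 2, the same subject would also leave the baseline, adverse event, device deficiency and deviation summaries.

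The trial is unblinded. Protocol 8.4.7 lets the investigator withdraw a subject for unmet criteria, which can happen after the arm is known. Two of the exclusions, prior AF and cardioembolic stroke, lie close to the endpoint. It is an inference, not something the documents state, that a detected AF episode could prompt a second look at them. The documents do not show that exclusions would differ by arm. The problem is that the SAP leaves the choice open, with only 23 events planned, so two analysts following it could report different primary populations.

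**Working it through.** **1. The passages side by side**

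| Place | What it implies for a randomized, ineligible subject |
|---|---|
| SAP 7.1.3, Enrollment Cohort | Not enrolled, so not in ITT if the ITT line uses this meaning |
| SAP 7.1.3, per-protocol criterion 1 | Not in ITT |
| SAP 7.1.3, ITT line with enrollment as in SAP 7.1.1 | In ITT |
| Protocol 12.1 (vii) | In the analysis |
| Protocol 8.3 and 8.4.7 | Stays in the assigned arm; data to exit used |

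The parenthesis opens with i.e., so it states what ITT is; it does not add a per-protocol-only criterion.

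**2. Can such subjects exist?** SAP 7.1.1 says "Once a subject is assigned to a study arm, he is considered eligible", but then plans that "Violation of inclusion and exclusion criteria at baseline will be summarized for all enrolled patients". With the 7.1.3 Enrollment Cohort as the denominator, that summary would be empty by definition. Protocol 8.4.7 lists one exit reason limited to subjects never randomized, "Subject did not meet inclusion/exclusion criteria and not randomized". Separately, it lists investigator withdrawal for unmet criteria, without that limit. The protocol therefore appears to foresee randomized subjects who did not meet the criteria.

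**3. The plan's own figures.** Inputs from protocol 12.1 (v) and SAP 6.1: event-free rates 92% and 98%, 496 enrolled, 2% lost before randomization, 10% attrition and 5% crossover a year in each arm, two-sided alpha 0.05, 85% power.

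- Hazard ratio: ln(0.92)/ln(0.98) = 4.13, as stated.
- Randomized: 496 × 0.98 = 486.1, as stated.
- Expected events at 486, from a Lakatos-type Markov model: 18.1 + 5.0 = 23.1, against 23 stated.

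Taking ITT as all randomized changes none of these.

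**4. Equal exclusion from both arms.** The excluded share p is assumed. At 85% power the noncentrality is 1.960 + 1.036 = 2.996, and power becomes Φ(2.996 × √(1 − p) − 1.960).

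| p | Subjects (486p) | Events (23p) | Power |
|---|---|---|---|
| 1% | 4.9 | 0.23 | 84.6% |
| 2% | 9.7 | 0.46 | 84.3% |
| 5% | 24.3 | 1.15 | 83.2% |

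The Lakatos-type model with two-way crossover gives 80.3% rather than 85% at 486 randomized. From that start the same exclusions give 79.9%, 79.5% and 78.3%, a similar loss.

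**5. Sensitivity to single events.** The 18 v 5 start is the rounded model split. With equal person-time assumed, z = (T − C)/√(T + C).

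| Monitoring v control | z | Two-sided p |
|---|---|---|
| 18 v 5 | 13/√23 = 2.711 | 0.007 |
| 16 v 5 | 11/√21 = 2.400 | 0.016 |
| 14 v 5 | 9/√19 = 2.065 | 0.039 |
| 13 v 5 | 8/√18 = 1.886 | 0.059 |
| 18 v 4 | 14/√22 = 2.985 | 0.003 |

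Significance is lost only after five monitoring-arm events and no control events are removed. Removing one control event moves the result the other way.

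**The case against.** The strongest reply is that one reading reconciles almost everything. The ITT line has no eligibility condition. Enrollment means consent in SAP 7.1.1 and protocol 7.2. If a subject assigned to an arm is deemed eligible, every randomized subject satisfies the parenthesis and it excludes nobody. Table 2 assigns no analysis to the Enrollment Cohort. Protocol 8.3 populates the assignment only after eligibility has been entered as verified, so few subjects should be affected. Protocol 12 and SAP 7.12 require departures from the planned methods to be reported. If ineligibility were unrelated to outcome, the pattern that loses significance (at least 5 of 18 monitoring-arm events and none of 5 control events removed) has probability of about 0.1% at 5% ineligible and 0.002% at 2%.

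Much of this stands. Including all randomized subjects is the better-supported reading, no passage orders removal, and the expected effect on power is small.

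It does not settle the point. The deeming sentence sits beside a plan to tabulate eligibility violations, so the SAP does not treat eligibility as closed at assignment. The reporting rules are weak protection, because an analyst applying the SAP 7.1.3 parenthesis could believe they were following the plan. The probabilities assume exclusion independent of outcome, which an unblinded trial cannot guarantee.

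**Conclusion.** The concern holds. SAP 7.1.3 contains wording that, taken literally, restricts ITT to eligible subjects. This conflicts with protocol 12.1 (vii) and with the consent-based enrollment in SAP 7.1.1 and protocol 7.2, and nothing in the SAP says which governs. It is an ambiguity with one conflicting reading, not an explicit exclusion rule.

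The size is probably small: 0.4 to 1.8 points of power if 1% to 5% are excluded equally from both arms, an assumed range because no rate is given. A reversed conclusion needs an extreme, one-sided removal from an event split that is itself illustrative. The case for change rests on pre-specification of the primary population in an unblinded trial, not on expected power loss. It should be fixed before the primary data snapshot.

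**What to change.** In SAP 7.1.3:

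- Define the Enrollment Cohort as all subjects who signed consent, matching SAP 7.1.1 and protocol 7.2.
- Define ITT as all randomized subjects in the arm assigned, whatever is later found about their eligibility.
- Delete the eligibility phrase from the parenthesis in the first per-protocol criterion.
- If an eligibility exclusion is wanted, make it a separate per-protocol criterion based on baseline information only.
- State that randomized subjects who exit for unmet criteria stay in ITT with data up to exit, consistent with protocol 8.4.7.

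The cost is SAP wording: no new data and no change to the sample size or event target. The SAP was written from protocol version 2 and the protocol is now version 4.0, so the change can be made when the two are aligned.

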8.4.3. Scheduled Follow-up Visits/CareLink Transmissions

After receiving notice of randomization assignment, Medtronic will provide the target dates and windows for each scheduled visit/CareLink transmission to the site. Should a subject miss a visit/transmission or the visit/transmission fall outside the pre-specified window, a study deviation must be reported and the original follow-up schedule maintained for subsequent visits/transmissions.

Data analyses include follow-up visits/CareLink transmissions, regardless of whether the visit occurs within the window; therefore, a late visit is preferred over a missed visit. Follow-up visit/CareLink transmission windows are listed in the Table 7 below and are based on days post randomization.

18 December 2018 Version 4.0 Page 32 of 66

Table 4: Follow-up Visit / CareLink Transmission Schedule

Study Follow-up Visit	Window (Calculated days post randomization) Window Start Target Window End			
	Willdow Start	raiget	Williadw Ella	
1 Month	23	30	37	
3 Month (CareLink Transmission)	76	91	106	
6 Month	168	183	198	
9 Month (CareLink Transmission)	259	274	289	
12 Month (1 year)	365	365	421	
18 Month	521	549	577	
24 Month (2 year)	702	730	758	
30 Month	887	915	943	
36 Month (3 year)	1067	1095	1123	

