### iv. Analysis Methods

Arrhythmic episodes recorded by the subject's inserted/implanted device or from external monitoring will be adjudicated by the adjudication committee to determine if they meet the primary endpoint definition. Only first detected and adjudicated AF episodes within 12-months (365 days) will be included for analysis. Each subject's time to first detected and adjudicated AF will be defined as the time from randomization date to the date of first documented AF (i.e. the date of event per Reveal LINQ ICM, ECG, etc.) to meet the primary endpoint definition, and Kaplan-Meier curves will be generated for each randomization arm. Subjects who have not experienced an AF endpoint through 12 months will be censored at:

(1) their point of last contact, usable Reveal LINQ ICM interrogation or CareLink transmission if they occur before or at 12 months, whichever is later

or

(2) 12 months if their point of last contact, usable Reveal LINQ ICM interrogation or CareLink transmission go beyond 12 months.

A two-sided log-rank test will be performed to compare the rates between arms. The 12-month survival estimate with its 95% confidence interval will be reported for each arm. The hazard ratio estimate for the treatment effect with its 95% confidence interval will be reported.

The types of monitoring (i.e., wired monitor, wireless monitor, etc.) used to identify AF events in the control arm may be reported to further characterize the events.

This document is electronically controlled. Printed copies are considered uncontrolled.

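### The supplementary per-protocol cohort drops subjects for crossover at any time, so a later departure can remove a subject whose AF event has already been counted

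*SAP*

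**What the plan says.** SAP 7.1.3 starts the PP cohort from the ITT cohort and applies two exclusions. The first is "Exclude subjects that cross-over to the other arm". The second is "Exclude subjects that are not programmed as follows at any point during the study (from CIP"), followed by five device settings. Neither refers to first AF, to censoring or to day 365.

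The primary endpoint does have a limit. SAP 7.9 states "Only first detected and adjudicated AF episodes within 12-months (365 days) will be included for analysis". Subjects are followed for up to 3 years (protocol 5.2), crossover is recorded whenever it occurs (protocol Table 2), and an explant at any time calls for a crossover form (protocol 8.4.6).

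SAP Table 2 lists PP beside ITT for both objectives. SAP 7.9 makes ITT the analysis cohort for each and PP an optional supplement. Protocol 8.3 leaves the PP definition to the SAP.

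Two other statements bear on timing. SAP 6.1, in the sample-size section, says the primary objective "will be analyzed considering data up to the 12 months follow-up visit for all subjects in the study at the time of the analysis". SAP 4.3 says "All objectives will be included in the final report using the final data snapshot".

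**The concern.** Membership of a cohort used to estimate time to first AF should not turn on what happens after that AF. Under the rule as written, a subject with AF in month 2 and an explant in month 20 may leave the PP cohort together with the event.

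Two things are at stake:

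- **Loss of events.** The plan is built on 23, so a supportive analysis has few to spare.
- **Bias.** The study is not blinded and the endpoint is AF detection, so the documents give no ground for assuming that device changes after AF are unrelated to AF or equal across arms.

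There is also a question of reproducibility. If late crossovers count, the PP result for the same 12-month endpoint could differ between the primary and the final snapshot, with no change in any subject's 12-month outcome.

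**Working it through.** **Inputs from the documents**

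- 486 randomized 1:1, so 243 per arm (SAP 6.1 and 5.3.1).
- One-year event-free rates of 92% and 98%, hazard ratio 4.13, 23 events required (SAP 6.1).
- "Annual Crossover rate = 5% (in each treatment group") and "Annual Attrition rate = 10% (in each treatment group"), both from SAP 6.1.
- 12-month visit window from day 365 to day 421 (protocol Table 4).
- Follow-up of 3 years (protocol 5.2).

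**Assumptions added here**

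- The planning crossover rate also applies after AF.
- Crossover has a constant hazard.
- AF times are uniform over year 1.

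**The plan's own figures**

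- Hazard ratio: ln(0.92)/ln(0.98) = 4.13, as stated.
- Expected year-1 events before attrition and crossover: 243 × 0.08 + 243 × 0.02 = 19.44 + 4.86 = 24.3. Allowing for 10% attrition and 5% crossover gives 23.1, in line with the plan's 23.

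**Events removed by a crossover that comes after AF**

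For AF at time u in years, the chance that the first crossover falls between u and T is 0.95^u − 0.95^T. The mean of 0.95^u over year 1 is 0.9748.

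| Crossover counted to | Mean probability | Events removed of 24.3 | With 10% attrition after AF |
|---|---|---|---|
| Day 365 | 0.9748 − 0.9500 = 0.0248 | 0.60 (0.48 ICM, 0.12 control) | 0.58 |
| Day 421 | 0.9748 − 0.9426 = 0.0322 | 0.78 | 0.75 |
| 3 years | 0.9748 − 0.8574 = 0.1174 | 2.85 (2.28 ICM, 0.57 control) | 2.51 |

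The last column treats attrition as a competing exit. With λ = −ln 0.95 and μ = −ln 0.90, it averages exp(−λu) · λ/(λ+μ) · [1 − exp(−(λ+μ)(T−u))] over u.

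**Effect on the hazard ratio if departure is unrelated to AF**

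The present rule removes the same fraction of subjects with and without AF. The rates stay at 8% and 2%, and the hazard ratio at 4.13. Total events kept, after all crossovers are removed, are 24.3 × 0.95 = 23.1 (year 1) or 24.3 × 0.95³ = 20.8 (3 years, before attrition).

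**Effect if departure follows AF and differs by arm**

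The documents give no rate for this, so the following shows sensitivity only. Suppose 25% of AF cases in the ICM arm were later removed.

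- PP rate in the ICM arm: 0.08 × 0.75/(1 − 0.08 × 0.25) = 0.06/0.98 = 6.12%.
- Hazard ratio: ln(1 − 0.0612)/ln(0.98) = 3.13.

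Removing 25% of control AF cases instead gives 0.02 × 0.75/(1 − 0.02 × 0.25) = 1.51% and a hazard ratio of 5.49. The direction is not fixed.

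**Two possible remedies, if departure is unrelated to AF**

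- *Exclude only for departures before AF or day 365.* AF cases are removed with mean probability 1 − 0.9748 = 0.0252, and AF-free subjects with probability 0.05. The ICM rate becomes 0.08 × 0.9748/(0.08 × 0.9748 + 0.92 × 0.95) = 8.19%. The control rate becomes 2.05% and the hazard ratio 4.12. This adds a small outcome dependence, because AF-free subjects have longer in which to be excluded.
- *Censor at departure.* Subjects contribute on equal terms up to departure, so the rates stay at about 8% and 2% and the hazard ratio at about 4.13. Events kept are 24.3 × 0.9748 = 23.7. Removals after AF, as in the sensitivity case above, no longer happen.

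**The case against.** **PP is optional and supplementary.** This is correct: ITT carries both objectives and nothing here touches either test. It limits the weight of the point. It does not make the rule sound, since Table 2 lists PP for both objectives and SAP 7.1.3 is the only place that defines it.

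**SAP 6.1 already limits the data to the 12-month visit.** This may hold for the primary objective. If so, the 3-year figures and the difference between snapshots largely fall away there. But that sentence explains a sample-size assumption and does not define PP membership. It also does not stop at the AF event or at day 365, since the visit may fall as late as day 421 and protocol 8.4.3 adds "Data analyses include follow-up visits/CareLink transmissions, regardless of whether the visit occurs within the window". Crossover after AF within year 1 remains in any case.

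**The programming bullet may mean something else.** It can be read as ever having departed from the settings, or as never having been so programmed. On the second reading later reprogramming excludes nobody. This stands, so the programming half of the point is conditional. The crossover bullet has no time limit on either reading.

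**A reader might infer that the PP hazard ratio is biased by a known amount or in a known direction.** The documents do not support that. They give no rate of reprogramming or of AF-related crossover, and the ratios of 3.13 and 5.49 above follow from assumed shares.

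**Conclusion.** The point holds as a minor one. The PP crossover rule, as written, allows an event after the outcome to decide membership, and no passage in either document prevents it. How often depends partly on whether an explant recorded on the crossover form counts as a PP crossover, which the SAP does not say.

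At the planning crossover rate, under constant hazards and with departure unrelated to AF, the cost is under one event on the year-1 reading and fewer than three on the 3-year reading, with the hazard ratio essentially unchanged. If departure follows AF and differs by arm, the PP hazard ratio is biased in a direction and by an amount that cannot be estimated from the documents.

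It would be tempting to conclude that the trial's main result is at risk. It is not, because both objectives are tested in the ITT cohort.

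**What to change.** In SAP 7.1.3, replace the undated exclusions with censoring:

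- Keep subjects who cross over or depart from the programming criterion in PP. Censor them at the departure date if it precedes both first adjudicated AF and the end of the objective's window (day 365 for the primary objective, end of follow-up for the secondary).
- Departures after first AF, or after the window, have no effect.
- Subjects who never received the assigned monitoring, or the required programming from the start, remain excluded.

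In the same edit, state that the programming criterion applies to subjects with an ICM, which meaning of its timing phrase is intended, and whether an explant recorded on the crossover form counts as a PP crossover.

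The cost is a few lines of wording. The analysis dataset must hold the dates of crossover and programming change; the form fields are not shown in the documents, so this should be confirmed. Censoring at departure may itself be informative if departure is related to AF risk, and the report should say so.
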